4.3 Subject Withdrawal and/or Discontinuation

Subjects are free to discontinue their participation in the study at any time without prejudice to further treatment. The investigator must withdraw any subject from the study at their request. Subjects should provide the reason for withdrawal and confirm whether they are withdrawing consent or withdrawing from IP treatment and will continue to participate in the study. The investigator or Allysta Pharmaceuticals, Inc., may withdraw the subject from IP treatment for any reason or if the subject meets any of the following criteria.

- Experiences a serious or intolerable AE that is judged by the investigator to preclude further study participation.
- Develops a clinically significant laboratory or other abnormality that is judged by the investigator to be potentially related to IP.
- Requires a medication that is prohibited by the protocol. Contact the Medical Monitor to discuss exiting a subject due to use of a prohibited medication before exiting the subject.
- Does not follow the protocol procedures, including noncompliance.
- Is lost to follow-up; every effort should be made to contact the subject.
- Administrative reasons, including termination of the trial by the Sponsor, unavailable for follow-up procedures.

- Experiences glaucomatous progression and/or unacceptable IOP elevation, per the discretion of the investigator.

Should a subject's medical or mental condition change or become unstable during the study, such that the ability of the subject to continue in this study becomes compromised or, in the investigator's judgment, their health is jeopardized, or further continuation is unadvisable, the subject may be withdrawn from study treatment and/or withdrawn from the study.

If a subject prematurely withdraws from the study, either at her/his request or at the discretion of the investigator or Allysta Pharmaceuticals, Inc. the reason for withdrawal should be recorded. All subjects prematurely discontinuing study dosing, regardless of cause, will return within 14 days from their last dose of IP to complete Early Termination visit assessments; consult the Medical Monitor to determine which diurnal measurements, if any, are required for the ET visit. Study subjects who withdraw from the study may be replaced at the Sponsor's discretion.

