4.4 Medication

During the washout period from prior IOP-lowering monotherapy, topical carbonic anhydrase inhibitors (CAI) (i.e., Dorzolamide (Trusopt®) or Brinzolamide (Azopt®) will be permitted, but will not be provided by the Sponsor. Should a topical CAI be employed during the washout period, the applicable washout for CAIs should be implemented and the CAI should be discontinued 5 days prior to Baseline (Day 0).

Current systemic medications which may influence intraocular pressure should be stable and not expected to change over the course of the trial. Should a subject's medical condition change or become unstable during the study, such that the change in non-ocular medication that can or may affect IOP are added or altered (i.e., steroids, systemic beta blockers, etc.), the subject's condition should be reviewed with the Medical Monitor prior to possible withdrawal from the study. If the subject is withdrawn, the subject will continue to be followed until he/she returns within 14 days from the last dose of IP to complete the Early Termination visit.

If, during the study, an investigator determines the IOP is inadequately controlled such that the safety of the subject is compromised, the PI may withdraw the subject from study treatment and institute IOP treatment.

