6 ASSESSMENT OF EFFICACY

6.1 Efficacy Parameters

Primary Efficacy Endpoints:

The primary efficacy measure will be the mean change in IOP from Baseline (Day 0) IOP (mmHg) for each group on Days 14 and 28 at each matched time point as compared to vehicle. IOP will be measured according to the Schedule of Assessments and Procedures Table.

Secondary efficacy endpoints:

1. The observed IOP, mean change from Baseline, and % change from Baseline IOP at each matched time point at each visit, and
2. The mean observed, mean change from Baseline and mean % change from Baseline for the mean diurnal IOP at each visit, and
3. The proportion of subjects reaching a target IOP (≤ 18 mmHg) at each time point and with the mean diurnal IOP for each visit. Each concentration will be compared to vehicle and the difference in means between treatment arms will be presented.

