6. HANDLING OF MISSING DATA

Missing data will not be imputed for efficacy assessments.

If intensity of an adverse event is missing the event will be considered severe. If relationship of adverse event to study drug is missing the event will be counted as related.

Adverse events will be considered treatment emergent unless it can be determined from the onset or end date information that the event cannot have been treatment emergent.

Other adverse events will be assumed to occur during the screening period.

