7.4 Intraocular pressure

The comparisons among treatment groups in IOP will be done for the various endpoints and time points. The outline of the analyses and groups is presented in Appendix 2.

For each visit in which IOP is measured descriptive statistics at each time point will be presented for the observed, change from baseline and % change from baseline values. In addition, at visits where five assessments are made descriptive statistics will be presented for the average of the observed values and the change from baseline and percent change from baseline where the values will be computed using average of five corresponding values at Day 0 as a baseline.

Descriptive statistics of IOP measures described above will be presented for the study eye, non-study eye and average of both eyes by time point and treatment group.

The 95% confidence intervals of the mean IOP by treatment group and time point and for diurnal IOP as well as for corresponding change from baseline will be presented.

For the IOP, diurnal IOP, and their change from baseline, each of the active treatment groups will be compared to the placebo group using the analysis of covariance (ANCOVA) model, separately for each time point. Baseline value will be used as a covariate. The difference between treatment groups in adjusted least-square means will be presented. Mean diurnal IOP will be presented as the mean of all values (including the 8 pm IOP value) (12-hour diurnal) and mean of all values up to the 4 pm IOP value (8 hour diurnal). If a subject is missing any time point for the calculation of the diurnal IOP, that subject will be excluded from the affected diurnal IOP analysis in the per protocol population.

The proportion of subjects reaching a target IOP (≤ 18 mmHg) at each time point and with the mean diurnal IOP for each visit will be presented by treatment group.

Within each dose level the change from baseline IOP will also be compared (a within subject comparison) with descriptive statistics.

Exploratory summaries may be presented to examine if treatment effects differ depending on iris color, age and baseline IOP.

Each comparison will be tested at the significance level of 0.05. No adjustments for multiple comparisons will be made.

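### The ITT proportion with IOP at or below 18 mmHg has no rule for subjects who stop for uncontrolled IOP or start other IOP treatment, so it can overstate the target rate in whichever arm those failures fall

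*SAP*

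**What the plan says.** Protocol 6.1 lists as its third secondary efficacy endpoint "The proportion of subjects reaching a target IOP (≤ 18 mmHg) at each time point", and likewise for the mean diurnal value, with each concentration set against vehicle. SAP 7.4 repeats it: "The proportion of subjects reaching a target IOP (≤ 18 mmHg) at each time point and with the mean diurnal IOP for each visit will" appear by arm. SAP Appendix 2 includes it at every post-baseline visit under H-1337 versus vehicle. Neither document gives a denominator or names a test for it.

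IOP failure is foreseen. If IOP is inadequately controlled, Protocol 4.4 says "the PI may withdraw the subject from study treatment and institute IOP treatment". SAP 7.1 pre-lists uncontrolled IOP as a reason for discontinuation. Protocol 4.3 then makes two statements about what follows. One describes subjects who are "withdrawing from IP treatment and will continue to participate in the study". The other reads "All subjects prematurely discontinuing study dosing, regardless of cause, will return within 14 days from their last dose of IP" for Early Termination (ET) assessments, with the Medical Monitor deciding which diurnal readings, if any, are needed.

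On missing values SAP 6 is brief: "Missing data will not be imputed for efficacy assessments". Protocol 8.5 takes the same position, giving the small exploratory design as the reason. The ITT population (SAP 5) is everyone treated who completes one on-therapy visit. Nothing there deals with readings taken after other IOP treatment has begun. The only rules that remove readings belong to the per-protocol population: optional exclusion of non-conforming visits and data points (SAP 5), and exclusion of subjects with an incomplete diurnal curve (SAP 7.4).

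**The concern.** A responder endpoint needs a rule for subjects whose outcome is settled by an event rather than by a reading. A subject taken off study drug because IOP was too high has not reached target on that drug. Followed as written, the plan never records that subject as a failure by rule.

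- **No reading at the visit.** With no imputation and observed values only, the subject drops out of that visit's proportion.
- **A reading taken on another hypotensive.** If it is measured and used, a value of 18 mmHg or less counts as success. This could happen because the subject stays on study, or because an ET reading is analysed as Day 28. ET shares the Day 28 column in the schedule, ET may fall up to 14 days after the last dose, and nothing says it precedes new treatment.

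At stake is the reading of a stated secondary endpoint in arms of 20, where one subject is worth 5 percentage points. Left open, the choice could be made after the data are unmasked.

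**Working it through.** **The plan's own figure.** The documents give no rate or power for this endpoint. The only efficacy power figure is for mean IOP (Protocol 8.1, SAP 4): 20 per group, difference 4.0 mmHg, SD 3.5 mmHg, two-sided alpha 0.05. The noncentrality is 4.0 / (3.5 × √(2/20)) = 3.61 on 38 degrees of freedom, giving 94.1% against the stated 94%. That figure reproduces and is unaffected by this point.

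**Inputs.** From the documents: n = 20 per arm and the 18 mmHg threshold. Assumed, because the documents give neither: r = 2 subjects truly at target, and w subjects failing for IOP, with w from 1 to 5.

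**Formulas for one arm.**

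- Failures counted as not at target: r / n
- Failures without a reading dropped: r / (n − w)
- All failures controlled to 18 mmHg or less on other treatment, measured and counted (upper limit): (r + w) / n

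| w | Counted as failures | Dropped | Counted as success (upper limit) |
|---|---|---|---|
| 1 | 2/20 = 10.0% | 2/19 = 10.5% | 3/20 = 15.0% |
| 2 | 2/20 = 10.0% | 2/18 = 11.1% | 4/20 = 20.0% |
| 3 | 2/20 = 10.0% | 2/17 = 11.8% | 5/20 = 25.0% |
| 5 | 2/20 = 10.0% | 2/15 = 13.3% | 7/20 = 35.0% |

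**Effect on a comparison.** Assume an active arm at 9/20 = 45% with no IOP failures, and three failures on vehicle. The SAP names no test, so Fisher's exact test is used for illustration only.

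- Counted: 45.0 − 10.0 = 35.0 points, p = 0.031
- Dropped: 45.0 − 11.8 = 33.2 points, p = 0.036
- Counted as success: 45.0 − 25.0 = 20.0 points, p = 0.32

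With a single vehicle subject counted as success (3/20), p is already 0.082.

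**The same gap in an active arm.** Assume 8/20 = 40% truly at target and three IOP failures there. Dropping them gives 8/17 = 47.1%; counting all three as successes gives 11/20 = 55.0%. The error now favours H-1337.

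**The case against.** The upper-limit column needs a chain of events: another hypotensive is started, IOP is measured on it, it is 18 mmHg or less, and the value is used. Several provisions make that less likely. Inclusion criterion 7 asks subjects to forgo all ocular hypotensives for the whole study. Protocol 4.3 lists need for a prohibited medication as grounds for withdrawal. It sends everyone who stops dosing to ET, so remaining in the study may mean only until that visit. This makes the route uncommon but does not close it: the 4.3 list concerns withdrawal from study drug and is permissive, and the SAP neither requires nor forbids using later readings.

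The denominator effect is small. In the example it is 1.8 points, less than one subject. That stands.

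The information is partly visible elsewhere. SAP 7.1 tabulates discontinuations for uncontrolled IOP and names prohibited medication as a possible major deviation, and SAP 7.6 lists concomitant medications. A reader could trace the cases, but none of this is a rule for the ITT proportion.

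Not imputing is also a reasoned choice for a small exploratory trial. It suits the IOP means better than a responder proportion, where the reason for stopping already tells us the outcome.

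A reader might infer that every failure who receives no other treatment leaves the denominator. That goes too far: a subject still measured above 18 mmHg is already correctly a non-responder. Only a subject with no value at that time point drops out, and even this is the natural reading of observed values without imputation rather than an explicit rule.

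**Conclusion.** The gap is real and worth closing before unmasking. For the target-IOP proportion in the ITT population, nothing classifies IOP failures, and the no-imputation rule gives a less suitable answer than counting them as not at target. On the assumed counts the rate is 10.0%, 11.8% or at most 25.0%, depending on handling. The first step is minor. The second could change how the comparison reads, but only if post-treatment IOP is both measured and used.

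A reader might infer that the gap systematically works against H-1337. The documents do not support this. They give no rescue, withdrawal or responder rates by arm, and the direction depends on where the failures fall. More failures on vehicle is plausible, but it is an assumption. Nor should 25.0% be read as an expected result: it takes three failures in 20, all brought to target on other treatment and all counted. It would also be wrong to say that such readings are held in the randomised group, because SAP 5 analyses subjects by the treatment actually received.

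The importance is moderate: a secondary endpoint, in a 28-day exploratory trial whose primary objective is safety.

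**What to change.** Add to SAP 7.4, as a stated exception to SAP 6 and Protocol 8.5:

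> For the ≤18 mmHg proportion in the ITT population, a subject who discontinued for uncontrolled IOP or started any non-study ocular hypotensive stays in the denominator and is counted as not at target at all later scheduled time points. Subjects missing a value for any other reason are not imputed, and the denominator is shown for each time point.

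The second sentence matters. Placing every ITT subject in the denominator without it would turn unrelated missing values, such as a missed time point or dropout for an adverse event, into silent failures.

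Also flag IOP readings taken after non-study IOP treatment starts. Under the rule, these subjects are classified the same way wherever an ET reading is placed.

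Separately, the two statements in Protocol 4.3, on remaining in the study after stopping study drug and on returning for ET, must be reconciled. No rescue rule is proposed and neither statement is preferred here.

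The cost is one exception to the no-imputation rule, and target rates that may be lower in arms with IOP failures. Discontinuation reasons and concomitant medications are already collected; applying the rule assumes that medication start dates are recorded with them. The SAP provides for amendment and is to be final before database lock and unmasking.

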7.5 Adverse Events

Treatment emergent adverse events (TEAE) are those with onset after randomization or if occurring prior to randomization worsened after randomization. Only treatment emergent events will be summarized. All events in the clinical database regardless of when they occurred will be provided in data listings. Adverse events will be classified according to the MedDRA system to the levels of System Organ Class (SOC) and primary Preferred Term (PT).

An overall summary will be presented which gives the number and percentage of subjects within each treatment group that experienced any TEAE, experienced any treatment related TEAE, permanently discontinued treatment due to a TEAE, experienced a treatment emergent SAE, and that died.

In summary tables, AEs occurring in both eyes will be counted once at the greater intensity and relationship to study drug.

Events that are possibly, probably or definitely related will be counted as an event related to study drug.

The number and percentage of subjects experiencing one or more events within a MedDRA system organ class and preferred term class without regard to intensity, relationship, or seriousness will be tabulated by treatment group. In addition, tables will display events by SOC, PT, and maximum intensity or closest relationship to treatment.

The number of deaths and SAEs will also be presented, and AEs leading to premature discontinuation from the study will be listed and tabulated.

A glossary listing that shows the verbatim terms assigned to each SOC and PT will be provided.

A listing of TEAEs by treatment group ordered by subject, SOC, PT, and onset date will be provided.

A listing of serious TEAEs by treatment group ordered by subject, SOC, PT, and onset date will be provided.

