7 ASSESSMENT OF SAFETY

7.1 Adverse Event Reporting

The investigator is responsible for monitoring the safety of subjects who have entered the study. Subjects should be asked at each visit about any changes in their health status. Any changes in health status after informed consent has been obtained, but prior to the first dose of IP, will be reported as medical history. AEs will be reported after the subject receives the first dose of IP (Day 0). Ongoing AEs at early termination or study completion (Day 28) will be followed until the event resolves, stabilizes, or for 30 days, whichever comes first.

All adverse events (serious and non-serious) must be documented regardless of the causal relationship to the study medication. The severity, frequency, seriousness, duration, relationship to IP(s), treatment of event, action taken with IP, and outcome for every adverse event should be documented in the source documents and CRFs.

Non-clinically significant incremental < 2 grade changes in conjunctival hyperemia (according to the photographic reference scale provided for the trial) are not required to be reported as adverse events.

To capture the most potentially relevant safety information during a clinical study, it is important that investigators record accurate AE terms on CRFs. Wherever possible, a specific disease or syndrome rather than individual associated signs and symptoms should be identified by the investigator and recorded on the CRF. However, if an observed or reported sign or symptom is not considered a component of a specific disease or syndrome by the investigator, it should be recorded as a separate AE on the CRF.

Investigators are required to report to Allysta Pharmaceuticals, Inc. or its representative all observed and/or volunteered AEs occurring during the clinical trial (21 CFR §312.64[b]) regardless of treatment group or suspected causality to the investigational drug.

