2. STUDY DESCRIPTION

2.1 Study Objectives

Primary Objective:

Evaluate the local ocular and systemic safety of three concentrations of H-1337 in subjects with POAG or ocular hypertension treated daily for up to 28 days.

Secondary Objectives:

Evaluate the ocular hypotensive efficacy of H-1337.

Evaluate the systemic pharmacokinetics of H-1337.

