2.3 Study Design/ Procedures

The study will evaluate the safety, tolerability, and preliminary efficacy of 3 concentrations of H-1337 and vehicle administered twice daily for 28 days. Up to 100 subjects, naïve to H-1337, will be randomized and dosed for 28 days. The parallel group, double-masked, placebo-controlled study will include the following dosing cohorts:

H-1337 0.06% (n=20)

H-1337 0.2% (n = 20)

H-1337 0.6% (n = 20)

Control (Vehicle) (n = 20)

Dosing will be BID unilaterally in the study eye for the first 3 days, then BID OU from Day 4 to Day 28.

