3. STUDY ASSESSMENTS/ENDPOINTS

Informed Consent: Properly executed informed consent (written and verbal) is to be obtained prior to completion of any study-related procedures. Subjects must review, sign, and date the informed consent document and receive a copy.

Medical and Ophthalmic History: Relevant and clinically significant medical and ophthalmic history must be recorded.

Concomitant Medications: All prescription and over-the-counter (OTC) medications and nutritional supplements taken during the study and 30 days prior to the Screening Visit will be recorded. Diagnostic eye drops do not need to be recorded.

Randomization: Randomization will be accomplished using an Interactive Web Response System (IWRS). Site personnel will receive instruction about IWRS access and use.

Adverse Events: Any events occurring after the first dose of IP will be recorded as an adverse event. At each visit, the subject should be asked questions such as, "How are you feeling? How are your eyes feeling today? Have you had any changes since the last exam?"

IP Administration and Compliance: The first dose of study IP will be administered to the study eye by study staff after the IOP measurement at T0 + 12 hrs. At Day 1/Visit 3 the AM dose of

study IP will be administered to the study eye by study staff after the IOP measurement at T0. Subjects will self-dose unilaterally until the Day 4 visit. At Day 4/Visit 4 the AM dose of study IP will be administered OU by study staff after the IOP measurement at T0. Subjects will self-dose OU for the remainder of the trial except on Day 14/Visit 5 (AM and PM doses) and Day 28/Visit 6 (AM dose) when study IP will be administered OU by study staff after the related IOP measurements. Compliance will be assessed at applicable visits by asking the subject about any missed doses. If the subject reports missing more than 4 doses since the prior visit, the subject will be counseled on IP compliance.

Heart Rate and Blood Pressure (BP) Measurements: Both systolic and diastolic blood pressure should be recorded.

Heart rate measurements will be measured by radial pulse. The subject should be in a seated and relaxed state. An automated blood pressure unit may be used to measure the heart rate.

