*Note: the non-study eye will not be treated until after T_0 on the Day 4 visit. Day 0 measures will be used as baseline for all time points for the non-study eye.

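### SAP 7.5 uses one subject-level start date and no by-eye adverse-event table, so in every arm fellow-eye events before that eye's first dose on Day 4 count as treatment-emergent

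*SAP*

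**What the plan says.** The dosing sequence is clear. SAP 2.3: "Dosing will be BID unilaterally in the study eye for the first 3 days, then BID OU from Day 4 to Day 28". On Day 0 the first dose is "administered to the study eye by study staff after the IOP measurement at T0 + 12 hrs" (SAP 3), which is the evening of that day. For the other eye, the notes in SAP Appendix 2 say that "the non-study eye will not be treated until after T_0 on the Day 4 visit". The schedule gives that visit a window of one day either way.

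SAP 7.5 does not carry this over to adverse events. A treatment-emergent event is defined by onset or worsening after randomization, with no reference to the eye ("Treatment emergent adverse events (TEAE) are those with onset after randomization or if occurring prior to randomization worsened after randomization"). The unit of the tables is the subject: "The number and percentage of subjects experiencing one or more events within a MedDRA system organ class and preferred term class", by treatment group. For bilateral events the rule is "In summary tables, AEs occurring in both eyes will be counted once at the greater intensity and relationship to study drug". SAP 6 treats events of uncertain timing as treatment-emergent and has no eye-specific rule.

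Other safety measures are tabulated by eye: visual acuity (SAP 7.12), hyperemia, slit-lamp and fundus findings and ocular symptoms (SAP 7.13), and pupil diameter (SAP 7.14). The adverse-event tables are not.

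The primary objective in SAP 2.1 is to "Evaluate the local ocular and systemic safety of three concentrations of H-1337".

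**The concern.** The objective asks two questions, local and systemic. A subject-level clock suits the systemic one, because drug exposure begins with the first drop in either eye. For the local question the exposed unit is the eye, and for the first few days only one eye is exposed. The tables cannot tell an event in a dosed eye from one in an eye that has had no drops.

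There are two routes into the tables. An event confined to the undosed fellow eye enters because nothing splits by eye. If the same event occurs in both eyes and is worse in the undosed one, the both-eyes rule lets the undosed eye set the subject's intensity.

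At stake are the ocular event rate in dosed eyes, which no adverse-event table would report, and the chance to compare event counts between a dosed and an undosed eye of the same subject over the unilateral days.

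**Working it through.** **Inputs.** T0 is 8 am (inclusion criteria). First study-eye dose: Day 0 after T0 + 12 h, so 8 pm. First fellow-eye dose: Day 4 after T0, so about 8 am, with a window of ±1 day. Last dose: Day 28 after T0. Planned size: 20 per arm. The documents give no background rate of ocular events, so 5% to 30% per subject in the fellow eye is assumed.

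**The plan's own safety figure.** SAP 4 says that an event not seen in 20 subjects has, with 95% certainty, a true incidence of at most 15%. The exact bound is 1 − 0.05^(1/20) = 13.9%; the rule of three gives 3/20 = 15%. The figure reproduces. It would also hold for a study-eye table, which has 20 study eyes per arm.

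**Share of time undosed.**

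- Dosing window: Day 0 8 pm to Day 28 8 am = 27.5 days.
- Undosed fellow-eye time: Day 0 8 pm to Day 4 8 am = 3.5 days; 2.5 if the visit falls on Day 3, 4.5 if on Day 5.
- Share of fellow-eye time: 3.5/27.5 = 12.7% (2.5/27.5 = 9.1%; 4.5/27.5 = 16.4%).
- Share of time in both eyes: 3.5/55 = 6.4%.
- SAP 7.5 sets no end to the treatment-emergent period, and Protocol 7.2 includes events reported up to 30 days after completion. Over 27.5 + 30 = 57.5 days the fellow-eye share is 3.5/57.5 = 6.1%.

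**Subjects affected.** Let p be the chance of a fellow-eye event over 27.5 days and w the undosed days. With a constant hazard the chance of an event while undosed is q = 1 − (1 − p)^(w/27.5), and the expected count per arm is 20q.

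| Assumed p | w = 2.5 | w = 3.5 | w = 4.5 |
|---|---|---|---|
| 5% | 0.09 | 0.13 | 0.17 |
| 10% | 0.19 | 0.27 | 0.34 |
| 20% | 0.40 | 0.56 | 0.72 |
| 30% | 0.64 | 0.89 | 1.13 |

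The range is about 0.1 to 1.1 subjects per arm; one subject is 1/20 = 5 percentage points.

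**Effect on the count of subjects with any event.** Some of these subjects have another event anyway. If a proportion r does, independently, the increase is q(1 − r). For w = 3.5 and r from 10% to 50%, it runs from 0.0065 × 0.5 = 0.3 points to 0.0444 × 0.9 = 4.0 points.

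**Effect on the comparison with vehicle.** If q is the same in both arms, the difference in proportions becomes [1 − (1 − r_A)(1 − q)] − [1 − (1 − r_V)(1 − q)] = (r_A − r_V)(1 − q). With q from 0.0047 to 0.0567 the difference shrinks by 0.5% to 5.7% of its size, with no shift in a fixed direction.

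**The case against.** The strongest reply is that a subject-level definition is defensible and conservative. From the Day 0 evening dose the subject is on study drug through the study eye, and systemic safety is part of the objective. Timing is not attribution: the investigator grades causality for every event (Protocol 7.9), SAP 7.5 tabulates by relationship, and listings with onset dates allow early events to be traced. This stands as a reason to keep the subject-level table. It does not supply an ocular rate in dosed eyes.

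Four stronger readings are tempting, and the documents do not support them.

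- A reader might infer bias against H-1337. The rule is the same for vehicle, and the fellow eye is undosed in all arms.
- A reader might infer that the plan throws away the dosed-versus-undosed comparison. It does not for graded signs: slit-lamp examination is scheduled on Day 1 and before T0 on Day 4, hyperemia grading before T0 on Day 4, and SAP 7.13 tabulates each eye. The gap is confined to adverse-event counts.
- A reader might infer that ocular and systemic events are simply pooled. Rows by system organ class separate them in part, though not by eye.
- A reader might expect the six Day 0 tonometry sessions to feed abrasions into the tables. They all precede the first dose, and Protocol 7.1 records pre-dose changes as medical history. Only an event arising after the evening dose would enter.

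The scenario in which the undosed eye sets the intensity is also narrow: it needs the same event in both eyes, worse in the undosed one.

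**Conclusion.** The point holds as a gap in the adverse-event tables. As written, SAP 7.5 counts fellow-eye events before that eye's first dose as treatment-emergent in all four arms, and no planned adverse-event table reports ocular events in dosed eyes. The consequence is modest, non-differential dilution. The time shares follow from the schedule, taking the nominal Day 28; the subject counts rest on assumed event rates, a constant hazard and, for the dilution factor, independence and equal background across arms. Clustering of events in the first days would raise the counts. Lower capture in the fellow eye would reduce them, and it is possible: Protocol 3.5 limits safety evaluation on Days 0 to 3 to the study eye, while Protocol 7.1 and 7.2 require every adverse event to be recorded. The change is worth making because safety is the primary objective and the cost is low, not because the planned comparison with vehicle would mislead.

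**What to change.** In SAP 7.5:

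1. Keep the subject-level summary, but start it at first dose, as Protocol 7.1 does, instead of at randomization.
2. Add tables of ocular treatment-emergent events for the study eye and the fellow eye separately, with onset or worsening judged against the first dose in the affected eye, and a separate table of non-ocular events.
3. Show fellow-eye events before that eye's first dose under an undosed-eye label, beside study-eye events of the same days.

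Reconcile Protocol 3.5 with Protocol 7.1 and 7.2 on whether fellow-eye events before Day 4 are sought and recorded. If the two eyes are not ascertained alike in those days, the between-eye display must say so.

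The cost is a few lines in the SAP, which is at version 1 and provides for amendment, and a few extra tables with sparse counts. No new data item should be needed, since the both-eyes rule already presupposes that the eye is recorded for each ocular event; this should be confirmed against the case report form.
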